8.4.3.3 Duration of Disease Control (DDC) using BICR/Investigator assessment and iRECIST 1.1

The analysis of endpoint for DDC described in Section 8.4.3.2 will be repeated for both the BICR and Investigator assessments using response based on the iRECIST guidelines.

8.4.3.4 Depth of response (DEoR)

DEoR is defined as the maximum percent reduction from baseline in tumor size reported in the CRF by the investigator and as reported by the BICR. Tumor size is defined as sum of target lesion diameter at that assessment reported in the CRF. The sum of target lesion diameter includes nodal (short axis) and non-nodal (longest axis) lesions.

Percent change in tumor size from baseline will be calculated at each scheduled tumor assessment. The maximum percent reduction (DEoR) per patient will be selected from the data specified as follows.

• For set, data up to and including first progression (PD)/first occurrence of objective tumor progression (i.e., the date of iUPD), provided that iCPD is confirmed at the next assessment until the day before first dose of add-on treatment, if there is

Statistical Analysis Plan (SAP) BNT111-01

Page 41 of 78 Version: Final v7.0 Date: 05Mar2024

add-on treatment, will be used. If there is no progression/objective tumor progression (progression of iRECIST), data until the day before first dose of add-on treatment, if there is add-on treatment, will be used.

- For Add-on treatment set, data from the date of first dose of add-on treatment up to and including first progression (PD)/first occurrence of objective tumor progression (i.e., the date of iUPD), provided that iCPD is confirmed at the next assessment, will be used for deriving DEoR. If there is no progression/objective tumor progression, all data from the date of first dose of add-on treatment will be used.
- Only data collected before the start of new anti-cancer therapy will be used.
- If there is an assessment (not the one after the first occurrence of PD based on RECIST 1.1/objective tumor progression based on iRECIST) on the same date as the start of new anti-cancer therapy, this assessment data will be used.

Tumor size will be summarized by scheduled visit (the details of visit mapping are in Section 10.7) and DEoR will be summarized using summary statistics by treatment group based on RECIST 1.1 and iRECIST for the randomized treatment and Add-on treatment.

In addition, DEoR for RECIST 1.1 and iRECIST will be illustrated by treatment using waterfall plots, separately for the set and Add-on treatment set, and listed in a patient data listing.

Additionally, spider plots for percent change of target lesions in sum of diameter from baseline will be presented by treatment based on RECIST 1.1 and iRECIST for BICR and investigator assessments based on and add-on treatment set. Only percentage change used for deriving DEoR will be displayed in the spider plots.

8.4.3.5 Analysis for Add-on Treatment Set

The analysis of endpoints ORR, DCR, DOR, TTR, PFS described in Sections 8.4.2.1, 8.4.2.2, 8.4.2.3, 8.4.2.4, 8.4.2.5 and 8.4.2.6 will be repeated for the Add-on Treatment set using the response for BICR and Investigator assessment based on the RECIST 1.1 and iRECIST guidelines. Per Section 8.1, these analyses will be based on data collected from the date of first dose of add-on treatment and after. For TTR and PFS, the starting date is the date of first dose of add-on treatment.

The analysis of DEoR for the add-on treatment set is in Section 8.4.3.4.

8.4.3.6 Overall Survival for arm 2 and arm 3

Analysis of OS will be performed for the BNT111 mono and cemiplimab mono treatment groups using the same method as Section 8.4.2.7 for the CCI set.

The analysis will be repeated for each of the following:

- Add-on treatment Set using the BNT111 + add-on cemiplimab and cemiplimab + add-on BNT111 treatment groups (the definition of overall survival will be the same as that in Section 8.4.2.7 e.g. starts from the date of randomization)
- The CCI set excluding patients that are in the Add-on Treatment set

Page 42 of 78 Version: Final v7.0 Date: 05Mar2024

An additional analysis would also be performed for the BNT111 + add-on cemiplimab and cemiplimab + add-on BNT111 treatment groups using the Add-on Treatment set. OS, for this analysis, would be defined as the time in months from date of first dose of add-on treatment to death from any cause.

Censoring rules are in appendix Table 5.2.

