The Safety set will be used for all safety analyses. The Add-on Treatment set will be used for analysis of both safety and efficacy data. Patients randomized to monotherapy (arm 2 and arm 3) who enter add-on treatment period are included in the analysis using both the mITT set, ITT set and the Add-on Treatment set, unless specified otherwise.

The following will occur for the analysis of ORR, DCR, DOR, TTR, PFS, OS, DEoR and EORTC endpoints and for the exploratory analysis of Duration of Disease Control (DDC):

- Tumor response endpoints ORR, DCR, DOR, DDC, TTR, DEoR and PFS: for the analysis using the set or set (sensitivity analysis for ORR (including DCR)), only the data until the day before first dose of add-on treatment will be used. For the analysis using the Add-on Treatment set, only the data from date of first dose of add-on treatment will be used.
- OS: for analysis using the set and Add-on Treatment set, all data would be used. For the exploratory analysis using the Add-on Treatment set (BNT111 + add-on cemiplimab and cemiplimab + add-on BNT111 treatment groups) the data from first day of add-on treatment would be used.
- For EORTC endpoints (Section 8.4.2.8) the summaries/analyzes will be performed as follows:
 - (i) While using set, data until the day before first dose of add-on treatment would be used.
 - (ii) In addition, a separate summary from first dose of add-on treatment to EOS, for the Add-on Treatment set.

All safety analyses will be based on the treatment actually received by the patient ('as treated'). All other analyses will be based on the treatment the patient was randomized to ('as randomized'), unless stated otherwise.

The following will occur for the analysis of safety data (apart from Adverse events)

- For the analysis of safety data using the Safety set, only data until the day before first dose of add-on treatment, if there is add-on treatment, or all data if there is no add-on treatment will be used.
- For the analysis of safety data using the Add-on Treatment set, only data from date of first dose of add-on treatment will be used.

The primary analysis of the trial will be performed based on all available data from a clinical data cut-off that will occur when all patients are randomized and response evaluable (i.e., having at least 3 post-baseline tumor assessments or discontinued before).

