8.4 Efficacy analyses

8.4.1 Primary analysis

The primary analyses will be performed using the CCI set.

Definition of primary endpoint

Overall Response Rate (ORR) defined as the proportion of patients in whom a CR or PR is observed as best overall response by blinded independent central review (BICR).

The BICR will provide a response for each patient assessment using the RECIST[©] 1.1 guidelines.

Main analytical approach

The primary statistical objective is to demonstrate that the ORR of BNT111+cemiplimab is greater than CCI using an overall significance level of CCI using an overall significance level of

[figure not shown]
The following null and alternative hypothesis are defined:

[figure not shown]
Statistical Analysis Plan (SAP) BNT111-01

Page 37 of 78 Version: Final v7.0 Date: 05Mar2024

The best overall response for a patient is defined as the best response across all responses prior to the start of new anti-cancer therapy for that patient. It is noted that a tumor response of SD can be confirmed from 36 days after first dose of study drug as the tumor assessment at week 6 (day 42) can be performed in a +/- 1 week window.

[figure not shown]
Statistical analysis

Additionally, a swimmer plot for duration on treatment and overall response assessments based on RECIST for BICR assessment will be presented based on set, add-on treatment set and combination of both (show both periods, including only for patients entering add-on treatment set). For IA1 the plot was generated for patients with BOR of CR/PR/SD and for IA2 the plot will be generated for patients with BOR of CR/PR/SD/PD/NE (for BICR data, the category Non-CR/Non-PD will be added). Tumor response and overall response will be listed.

Sensitivity analysis

Additionally, sensitivity analysis based on confirmed CR/PR (RECIST 1.1) for BICR assessment for the CCI set will be performed.

Page 38 of 78 Version: Final v7.0 Date: 05Mar2024

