8.4.2.2 Disease Control Rate (DCR) using BICR and RECIST 1.1

DCR is defined as the proportion of patients in whom a CR or PR or SD (for BICR data, the Non-CR/Non-PD response will be included in the DCR, similarly to SD response) (SD assessed at least 6 weeks [+/- 1 wk] after first dose) is observed as best overall response. Patients not meeting the criteria for CR or PR or SD (for BICR data, the Non-CR/Non-PD response will be included), including those without any post-randomization tumor assessments, will be considered as non-responders. Only patients with adequate (i.e. available) baseline and post-baseline assessments, in whom a CR, PR or SD is observed will be analyzed.

DCR will be summarized as a binary endpoint along with ORR (Section 8.1).

If the sensitivity analysis of ORR for the CCI and CCI and is done then a summary of DCR will also be included.

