8.4.2.5 Progression Free Survival (PFS) using BICR and RECIST 1.1

PFS is defined as the time in months from randomization to first objective tumor progression (PD according to BICR and RECIST 1.1), or death from any cause, whichever occurs first. PFS will be calculated as: Date of first objective PD or death - Date of randomization + 1.

PFS will be analyzed as a time-to-event endpoint. Patients alive and without disease progression or patients lost to follow-up at data cut-off date will be censored per the censoring rules in Table 5.1.

PFS will be analyzed as a time-to-event endpoint (Section 8.1).

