10.5 Appendix 5: Censoring rules

Table 5.1 Censoring Rules for PFS, DOR & DDC Based on Food & Drug Administration (FDA) Guidelines

For calculation of 2 or more missed consecutive scheduled assessments, see the text after the censoring rules tables.

If a subject met multiple censoring criteria, the earliest censoring date will be used.

Situation (Censoring Order)	Date Patient Has Event or is Censored	Situation Outcome
Inadequate baseline assessment* (1)	Randomization date	Censored
Inadequate post-baseline assessments* (2)	Randomization date	Censored
* Not applicable to DOR and DCR		
Progression documented on or between scheduled tumor assessments	Date of first objective tumor assessment showing objective progression	Progressed (Event)
Progression documented not after 2 or more missed consecutive scheduled assessments during the treatment period or not after 1 or more missed scheduled assessments during the Follow-up period	For RECIST 1.1, the Date of objective progression / for iRECIST, the date of iUPD if progression associated with that iUPD has been confirmed.	Progressed (Event)
Death (and progression has not occurred previously) not after 2 or more missed consecutive scheduled assessments during the treatment period or not after 1 or more missed scheduled assessments during the Follow-up period	Date of death	Death (Event)

Statistical Analysis Plan (SAP) BNT111-01

Page 71 of 78 Version: Final v7.0 Date: 05Mar2024

Situation (Censoring Order)	Date Patient Has Event or is Censored	Situation Outcome
Death without objective progression	Date of death	Death (Event)
Death or progression after 2 or more consecutive missing scheduled assessments during the treatment period or after 1 or more missed scheduled assessments during the Follow-up period (3)	Date of last adequate assessment with evidence of no progression; if no adequate assessment exists then censored at the randomization date.	Censored
New anti-cancer therapy started prior to progression or death (4)	Date of last adequate assessment with evidence of no progression before anti-cancer therapy; if no adequate assessment exists then censored at the randomization date	Censored
No progression or death (6)	Date of last adequate assessment with evidence of no progression; if no adequate assessment exists then censored at the randomization date	Censored

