10.7 Appendix 7: Algorithm for visit window mapping of tumor assessments for depth of response

All data points for tumor assessments will be used. This section explains how to assign visits to the assessments for the depth of response analysis.

Data is collected by evaluation number. This evaluation number will be used to group assessments/records for same targeted visit. The tumor assessment data, including unscheduled visit data, will be mapped per the details described below:

Derive AVISIT1/AVISIT1N based on tumor assessment date.

- Calculate trial day of tumor scan performed referenced to first dose date.
- Define target assessment day and analysis window range (lower and upper limits) based on protocol specified schedule.
- Check where the calculated trial day falls and assign AVISIT1.
- AVISIT1N will represent week number of the derived visit (numeric part of AVISIT1).
- For the summary analysis by visit, the assessment closest to the target day will be analyzed. In case, 2 assessments are equidistant, the earliest assessment will be used in the analysis.

Some illustrative examples:

AVISIT1	AVISIT1N	AWTARGET1 (Analysis Window Target)	AWLO1 (Analysis Window Beginning Timepoint)	AWHI1 (Analysis Window Ending Timepoint)
Screening	0	-28	-28	-1
Week 6	6	43	1	63
Week 12	12	85	64	116
Week 21	21	148	117	179
Week 30	30	211	180	242
Week 39	39	274	243	305
Week 48	48	337	306	378
Week 60	60	421	379	462
Week 72	72	505	463	546
Week 84	84	589	547	630
Week 96	96	673	631	714
Week 108	108	757	715	798
Add-on Week 6	1006	43	1	63
Add-on Week 12	1012	85	64	116
Add-on Week 21	1021	148	117	179
Add-on Week 30	1030	211	180	242
Add-on Week 39	1039	274	243	305
Add-on Week 48	1048	337	306	378
Add-on Week 60	1060	421	379	462
Add-on Week 72	1072	505	463	546
Add-on Week 84	1084	589	547	630
Add-on Week 96	1096	673	631	714
Add-on Week 108	1108	757	715	798

Page 78 of 78 Version: Final v7.0 Date: 05Mar2024

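### The add-on PFS clock starts at first add-on dose, but the fallback censoring date and the minimum interval for stable disease keep their main-period anchor (minor; exploratory endpoints)

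*SAP*

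**What the plan says.** - **Time origin.** SAP 8.4.2.5 defines the main analysis: "PFS will be calculated as: Date of first objective PD or death - Date of randomization + 1". SAP 8.4.3.5 repeats it for the Add-on Treatment Set with a new origin: "For TTR and PFS, the starting date is the date of first dose of add-on treatment".
- **Data cut.** For tumor endpoints in that set, SAP 8.1 says "only the data from date of first dose of add-on treatment will be used".
- **Censoring.** Table 5.1 (SAP 10.5) is the only censoring table for PFS, DOR and DDC and has no add-on version. Inadequate baseline or post-baseline assessment leads to censoring at randomization. Several other rows carry the same fallback: "if no adequate assessment exists then censored at the randomization date". Where censoring rules compete, "If a subject met multiple censoring criteria, the earliest censoring date will be used".
- **Stable disease.** SAP 8.4.1 says "a tumor response of SD can be confirmed from 36 days after first dose of study drug". The DCR definition in 8.4.2.2 has "SD assessed at least 6 weeks [+/- 1 wk] after first dose", and the DDC definition in 8.4.3.2 uses the same condition. None has an add-on form.
- **Visit windows.** Appendix 7 (SAP 10.7) instructs: "Calculate trial day of tumor scan performed referenced to first dose date". Its table nevertheless has separate rows from Add-on Week 6 to Add-on Week 108, which restart at day 1.
- **Missed scans.** SAP 10.5 sets limits for the first 3 months, the next 9 months and thereafter, without saying from which date the periods run.

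**The concern.** When an endpoint is repeated with a new time origin, every date rule that feeds it has to move to the same origin. Here the PFS start moves, but the fallback censoring date stays at randomization, which precedes the new start. The resulting duration is impossible. The stable-disease minimum exists so that a very early scan cannot count as disease control; measured from the original first dose, it has already elapsed when add-on begins. Anti-tumor activity during add-on is a stated exploratory objective, so its PFS and DCR tables should be derivable from the rules as written.

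**Working it through.** **Inputs.** The PFS formula and its add-on origin (SAP 8.4.2.5, 8.4.3.5); the fallback date (Table 5.1); the 36-day minimum (8.4.1); the windows (Appendix 7); 1 month = 30.4375 days (8.1). The trial day A of the first add-on dose is not in the documents and is assumed: 120 as the example, 37 to 547 as the range. Randomization and first dose are both taken as trial day 1. Add-on Day d is then trial day A + d − 1.

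**The plan's own figures.** Window targets are 7 × week + 1, so week 6 is day 43 and week 12 is day 85. Limits are midpoints between targets: (43 + 85)/2 = 64, so week 6 ends on day 63; (85 + 148)/2 = 116.5, so week 12 ends on day 116. The stable-disease minimum is day 43 − 7 = day 36. All agree with the SAP.

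**1. Censoring date.** Take a patient who is alive and has no adequate post-add-on scan. The data cut excludes monotherapy scans, so the fallback applies and the censoring date is day 1.

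PFS = 1 − A + 1 = 2 − A

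| First add-on dose (trial day) | PFS as written | Months |
|---|---|---|
| 37 | −35 d | −1.15 |
| 78 | −76 d | −2.50 |
| 120 | −118 d | −3.9 |
| 211 | −209 d | −6.87 |
| 365 | −363 d | −11.93 |
| 547 | −545 d | −17.91 |

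The value is negative for any A of 3 or more. Censoring at first add-on dose instead gives A − A + 1 = 1 day. The tie rule does not help, because randomization is the earliest date available. Only survivors are counted here: Table 5.1 also has a row that makes death without progression an event on the date of death.

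A patient censored on Day 1 and a patient with a negative time are both absent from every later risk set, so the Kaplan-Meier median does not change. Listings and minimum times are wrong. The censored and at-risk counts may be, depending on how the program treats negative times.

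**2. Minimum interval for stable disease.** With A = 120, a scan on add-on Day 15 is trial day 120 + 15 − 1 = 134. Since 134 ≥ 36, stable disease qualifies as written; counted from first add-on dose, 15 < 36 and it does not. If A ≥ 36, every add-on scan passes. The first scheduled scan on monotherapy falls no earlier than day 36, so an add-on start before then would need an extra scan.

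Best overall response is the best across all responses, so stable disease on Day 15 followed by progression at add-on week 6 becomes disease control. Scheduled add-on scans start at 6 ± 1 weeks (add-on Day 36 at the earliest) and pass either way. Only extra scans before that day matter. The protocol allows them when clinically indicated, and SAP 8.1 counts unscheduled scans for tumor response.

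**3. Appendix 7 reference line.** An on-time add-on week-6 scan (add-on Day 43) is trial day 120 + 43 − 1 = 162. Referenced to the original first dose, it falls in the 117–179 window, a week-21 row. Referenced to first add-on dose, it falls in 1–63, Add-on Week 6.

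**4. Missed-scan periods.** The limits for two missed scans are 2×6×7 + 14 = 98 days, then 2×9×7 + 14 = 140, then 2×12×7 + 28 = 196; across the change after the first 3 months the limit is 6×7 + 9×7 + 14 = 119. A 120-day gap early in add-on exceeds 98 and 119 if the periods restart at add-on, but not 140 if they run from the original start and the patient is in the 9-month period. A progression or death after that gap is censored on the first reading and an event on the second.

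**The case against.** The best defense is that the intent is plain. Appendix 7 has its own add-on rows with the same limits as the main rows. They make sense only with first add-on dose as day 1, since day 43 would otherwise belong to both Week 6 and Add-on Week 6. The scan schedule also restarts at add-on start (schedule of activities for add-on treatment). This stands. A reader might infer that nearly every add-on scan will be filed under the wrong week, but the documents do not support that: one line was left unadapted. Appendix 7 also serves only the by-visit tumor-size summary, not the response endpoints.

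The stable-disease rule may be settled elsewhere. SAP 8.1 refers to a separate programming guideline for best overall response, which is not available here, and the 36 days are justified by a week-6 scan whose schedule restarts at add-on. This also stands as a reservation. However, the SAP does not cite that guideline for PFS censoring or visit windows. Where the SAP means the add-on period, it generally says so: data cut and baseline (8.1), depth of response (8.4.3.4), overall survival (8.4.3.6), exposure (8.5.1) and treatment-emergent events (8.5.2). Silence in Table 5.1 and in the stable-disease rule therefore reads as an omission.

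A negative time would also be noticed in programming, and SAP 8.1 defines the table N as the size of the analysis set, so patients need not vanish from N. Both points are fair and limit the consequence. Neither supplies the correct censoring date.

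**Conclusion.** The point holds, at minor severity. Table 5.1 as written gives impossible add-on PFS values for surviving patients without an adequate post-add-on scan. The stable-disease minimum as written has no effect in the add-on period once add-on starts on trial day 36 or later, unless the programming guideline says otherwise. The Appendix 7 line and the missed-scan periods need only clarification.

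The number affected cannot be derived. Arms 2 and 3 have 90 patients planned, which is the ceiling for the add-on set; the plan states neither uptake nor the share without a scan. Purely as an assumption, 10–20% without a scan would be 6–12 of 60 add-on patients, or 9–18 of 90. The stable-disease rule affects only patients whose stable disease rests on an extra scan before add-on Day 36.

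A reader might infer that add-on results in general are wrong, or that the trial's main conclusion is at risk. Neither follows. These rules leave add-on ORR and TTR unaffected. DOR is largely unaffected: it is exempt from the two inadequate-assessment rows, and responders have an adequate scan. Add-on overall survival uses Table 5.2. The add-on endpoints are exploratory with no formal comparison between groups, and the primary ORR in Arm 1 is untouched.

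**What to change.** Add one sentence to SAP 8.4.3.5:

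> *For all tumor-endpoint analyses of the Add-on Treatment Set, the date of first add-on dose takes the place of the randomization date and the first dose date in Table 5.1, in the minimum interval for stable disease (DCR and DDC), in the missed-assessment periods of Section 10.5, and as the reference day for the add-on rows of Appendix 7.*

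Check the best-overall-response programming guideline against this sentence and align it if needed. The cost is that sentence and a change of reference date in the add-on programs. Add-on DCR may come out slightly lower; the primary analysis does not change.

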	 Occurrence of abnormal vital signs parameters within a patient.

Clinical Trial Protocol BNT111-01

Page 43 of 133 Version: 7.0 Date: 09 FEB 2023

Objectives	Endpoints
Assess health-related quality of life (HRQoL) of patients treated with BNT111 + cemiplimab (Arm 1) and of patients receiving BNT111 and cemiplimab as single agents as measured by the European Organization for Research and Treatment of Cancer Quality of Life Questionnaire Core 30 items (EORTC QLQ-C30).	 Mean changes from baseline in the global health status score of the EORTC QLQ-C30*. Mean changes from baseline in scores of the EORTC QLQ-C30 functional and symptoms scales*. Time to first clinically meaningful deterioration in global health status score as measured by EORTC QLQ-C30*. Time to first clinically meaningful deterioration in symptoms and functioning as measured by EORTC QLQ-C30*.
Exploratory objectives	
Assess the anti-tumor activity of BNT111 + cemiplimab (Arm 1) and each single agent (i.e., monotherapy of BNT111 and cemiplimab) according to iRECIST.	 ORR, DOR, DCR, TTR, PFS as assessed by BICR and the investigator.
Assess additional measures of antitumor activity of BNT111 + cemiplimab (Arm 1), and each single agent (i.e., monotherapy of BNT111 and cemiplimab) according to RECIST 1.1 / iRECIST.	 Depth of response as defined by maximum percentage reduction from screening/baseline* in the size of the tumor as assessed by BICR and the investigator.
Assess the anti-tumor activity during add-on BNT111 + cemiplimab (Arm 2 and 3) according to RECIST 1.1/ iRECIST.	 ORR, DOR, DCR, TTR, PFS as assessed by BICR and the investigator.
Assess OS of each single agent (i.e., BNT111 and cemiplimab) with or without add-on treatment (Arm 2 and 3).	• OS.
Assess systemic induction/expansion of BNT111 antigen-specific T cells.	Patients in biomarker sub-study (selected trial sites): Occurrence of de novo induction of increase in expansion of BNT111 antigen-specific T cells under treatment compared to screening/baseline* (Arms 1 and 2 and add-on treatment).

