5.1.3 Inclusion criteria for entering add-on therapy

- 1. Patients must have confirmed disease progression on monotherapy in Arm 2 or 3 of the trial.
 - a. An initial radiological progression needs to be verified by BICR.
 - Radiological progression to be confirmed by two scans 4 to 12 wks apart unless initial progression is accompanied by new symptoms, or deterioration of PS not attributed to toxicity, in which case one scan is sufficient.
- 2. Patients must sign a new ICF to continue with add-on therapy. Informed consent must be documented before any add-on-specific procedure is performed.
- 3. WOCBP must have a negative serum (beta-hCG) at baseline. Patients that are post-menopausal or permanently sterilized can be considered as not having reproductive potential. For a definition of WOCBP, see Section 10.4.
- 4. Female patients of reproductive potential must agree to use adequate contraception during and for 6 months after the last trial drug administration (Section 10.4).
- 5. WOCBP must agree not to donate eggs (ova, oocytes) for the purposes of assisted reproduction during trial starting at screening, during the trial and for 6 months after receiving the last trial treatment.
- 6. A man who is sexually active with a WOCBP and has not had a vasectomy must agree to use a barrier method of birth control, e.g., either condom with spermicidal foam/gel/film/cream/suppository or partner with occlusive cap (diaphragm or cervical/vault caps) with spermicidal foam/gel/film/cream/suppository, and all men must also not donate sperm during the trial and for 6 months after receiving the last trial treatment. For a definition of adequate contraception, see Section 10.4.

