7 ANALYSIS SETS AND SUBGROUPS

7.1 Analysis sets

The following analyses sets are defined:

Table 7.1 Analysis Sets

Analysis Set	Description
Screened	The screened set is defined as all patients who signed informed consent.
Intent to treat	The Intent To Treat (ITT) set is defined as all patients who are randomized.
Modified intent to treat	The modified Intent To Treat (mITT) set is defined as all patients who are randomized, had at least one dose of trial treatment and have a baseline and at least one post-randomization tumor response assessment.
Add-on Treatment Set	The Add-on Treatment Set is defined as patients who received at least one dose of Add-on treatment
Safety	The safety set is defined as all patients who received trial treatment (i.e., at least one dose of BNT111 or cemiplimab).
Per protocol	The Per protocol Set (PPS) is defined as all patients who received trial treatment and fulfil the following criteria:
	 The absence of any important protocol deviations that could affect the primary efficacy analysis. The completion of a minimal exposure to the treatment of 1 cycle i.e. the patient should receive all the treatment doses planned as per schedule of assessment for at least 1 cycle. Availability of baseline and at least one on-treatment / post-randomization tumor assessment. Important deviations will lead to an exclusion of patients from the PPS and will be agreed at the data review meeting prior to database snapshot for the primary analysis.

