8.4.2.7 Overall Survival (OS) for combination arm

OS is defined as the time in months from randomization to death from any cause. OS will be calculated as: Date of death - Date of randomization + 1.

OS will be analyzed using Kaplan-Meier methodology for BNT111 + cemiplimab treatment group. Patients alive or patients lost to follow-up at data cut-off will be censored per the censoring rules in Table 5.2.

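### SAP 8.4.3.6: the OS curves with and without add-on, both counted from randomization, are not comparable, and the add-on curve is inflated by guaranteed survival time

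*SAP*

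**What the plan says.** Protocol section 3 lists as an exploratory objective: "Assess OS of each single agent (i.e., BNT111 and cemiplimab) with or without add-on treatment (Arm 2 and 3"). SAP 8.4.3.6 serves it with four Kaplan-Meier summaries for Arms 2 and 3:

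1. OS of each whole arm as randomized, using the SAP 8.4.2.7 definition: "OS is defined as the time in months from randomization to death from any cause".
2. OS in the Add-on Treatment Set, where "the definition of overall survival will be the same as that in Section 8.4.2.7 e.g. starts from the date of randomization".
3. OS in the main analysis set (name redacted) after removing those patients: "set excluding patients that are in the Add-on Treatment set".
4. OS in the Add-on Treatment Set once more, "defined as the time in months from date of first dose of add-on treatment to death from any cause". SAP 8.1 says of this one that "the data from first day of add-on treatment would be used".

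Membership is set in SAP 7.1: "The Add-on Treatment Set is defined as patients who received at least one dose of Add-on treatment". Protocol 5.1.3 and 5.1.4 say what must happen first. Progression on monotherapy is verified by BICR. "Radiological progression to be confirmed by two scans 4 to 12 wks apart unless initial progression is accompanied by new symptoms" or worsening performance status. The patient signs a new consent, meets the add-on exclusions, and starts no later than 6 weeks after confirmed progression.

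SAP sections 4 and 8.1 disclaim formal comparisons between treatment groups, though 8.1 leaves room for an exploratory comparison of time-to-event endpoints. SAP 5.2 lists the 8.4.3.6 OS analysis among the IA2 outputs. Nothing in 8.4.3.6 mentions delayed entry, a landmark, a time-dependent method or a caution on reading summaries 2 and 3 together.

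**The concern.** Summaries 2 and 3 divide each calibrator arm by something that happens after randomization, but start the clock at randomization. Nobody in the Add-on set can die before the first add-on dose, yet all the time up to that dose is credited to the set. Patients who die or become ineligible before add-on go into summary 3. So do patients who progress and decline it, and those who never progress and so never qualify. Summary 3 therefore describes neither single-agent treatment nor a population in which add-on was unavailable.

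The SAP avoids this for other endpoints. For TTR and PFS in the Add-on set, section 8.4.3.5 moves the start to the first add-on dose, and summary 4 does the same for OS.

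What is at stake is how the add-on results are read. Summaries 2 and 3 are the outputs that split OS in the terms of the objective. Side by side, they can appear to show that adding the second drug changes survival when it does nothing.

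**Working it through.** **Figure to reproduce.** The documents give no OS event count, power, hazard ratio or expected add-on share. The only related figure is the arm size: 180 × 1/4 = 45 per calibrator arm, as in SAP Table 3.2.

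**Guaranteed survival time.** Inputs are the scan schedule (first scan at 6 ± 1 weeks, SAP Table 3.2), the confirming scan 4 to 12 weeks later (Protocol 5.1.3) and the limit of 6 weeks to start (Protocol 5.1.4).
- Earliest on scheduled scans, one symptomatic scan: 6 − 1 = 5 weeks.
- Week-6 scan, shortest confirmation: 6 + 4 = 10 weeks.
- Week-6 scan, longest confirmation and latest start: 6 + 12 + 6 = 24 weeks.

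Progression seen at a later scan adds to this.

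**Simulation with no add-on effect.** Progression occurs at time P. Death occurs at D0 if D0 < P, otherwise at P + D1. Add-on start is A = first scheduled scan after P + confirmation delay + gap. The patient has add-on if still alive at A and a chance draw with probability equal to the uptake succeeds. The naive hazard ratio (HR) is from a Cox model of ever-add-on versus the rest, both from randomization.

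Assumptions, none given in the documents:
- exponential times, with median time to progression 3 months;
- 25% of progressions confirmed on one scan, the rest 4 to 12 weeks later, with a gap of up to 6 weeks;
- 36 months of follow-up, 6,000 patients per scenario.

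Median add-on start came out at 5.3 to 6.0 months. Selected scenarios, add-on versus rest:

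| Median survival before / after progression (months) | Never progress | Uptake | Median OS (months) | 6-month survival | Naive HR |
|---|---|---|---|---|---|
| 12 / 12 | 0% | 40% | 18.7 vs 9.2 | 0.93 vs 0.62 | 0.59 |
| 12 / 12 | 0% | 80% | 18.7 vs 4.9 | 0.94 vs 0.43 | 0.38 |
| 60 / 10 | 0% | 50% | 17.6 vs 10.8 | 0.94 vs 0.71 | 0.65 |
| 60 / 10 | 0% | 80% | 17.6 vs 7.5 | 0.93 vs 0.59 | 0.46 |
| 60 / 10 | 10% | 50% | 17.0 vs 13.3 | 0.93 vs 0.75 | 0.91 |
| 60 / 10 | 20% | 50% | 17.1 vs 15.7 | 0.93 vs 0.78 | 1.12 |
| 60 / 10 | 30% | 50% | 17.4 vs 19.3 | 0.93 vs 0.81 | 1.32 |
| 60 / 6 | 30% | 90% | 13.5 vs 14.9 | 0.88 vs 0.71 | 1.74 |
| 60 / 18 | 10% | 50% | 26.2 vs 21.1 | 0.96 vs 0.82 | 0.85 |
| 60 / 18 | 30% | 50% | 25.9 vs 27.9 | 0.96 vs 0.86 | 1.10 |

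In the first two rows true median OS is 12 months for everyone, so the add-on curve is too long by 18.7 − 12 = 6.7 months. Over all scenarios with higher mortality after progression, the HR is 0.46 to 0.65 when nobody stays progression-free. It is 0.71 to 0.91 at 10%, 0.97 to 1.31 at 20%, and 1.10 to 1.74 at 30%. At 20% the median and the HR can point in opposite directions. Six-month survival favours add-on in every run.

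**Check of two remedies, still with no add-on effect.**
- Time-dependent add-on status from randomization: HR 1.01 to 1.04 with constant hazard, but 1.15 to 4.30 when mortality is higher after progression.
- Progressors only, clock from the scan showing progression, add-on time-dependent (20,000 patients, four scenarios): HR 1.01, 1.01, 1.00 and 1.03. The naive HRs in the same runs were 0.49, 0.88, 1.35 and 1.47.

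**The case against.** The best defence is that the SAP does not compare these curves. It repeats a Kaplan-Meier summary in several sets, disclaims formal comparison, and also provides whole-arm OS and OS from first add-on dose. The objective is exploratory, the arms have 45 patients each, and nothing here touches ORR. All of that stands. A reader might infer that 8.4.3.6 specifies a test of add-on against no add-on. It does not. The contrast is inferred from the objective's wording and from the exploratory comparison that 8.1 permits.

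A reader might also infer that the pair of curves must show an add-on benefit. The documents do not support that either. Patients who never progress stay in the remainder and live longer, so the bias can cancel or reverse. The documents give no share for them. Protocol 4.2 does expect limited monotherapy activity, which makes a spurious benefit plausible but does not establish it.

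Two further cautions stand. Delayed entry or time-dependent status from randomization (a Simon-Makuch curve) looks like the natural repair. It sets add-on patients, all of whom have progressed, against a group made up largely of patients still progression-free, and so creates apparent harm. Summary 4 has no guaranteed time, but it has no comparator and starts after progression. It should not be set against whole-arm OS from randomization.

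The defence does not remove the main problem: summary 2 credits add-on with time in which death was impossible, and no text warns the reader.

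**Conclusion.** Summary 2 is biased upward as a description of survival with add-on. This follows from the set definition and the time origin, without any simulation. Summaries 2 and 3 cannot be interpreted against each other. With no add-on effect, early survival favours add-on, while the overall contrast may show a large benefit, nothing, or a reversal (HR 0.38 to 1.74 over the assumed scenarios with uptake of 40% to 90%). The size depends on progression, survival, uptake and the share who never progress. All of these are assumptions here, so the ranges illustrate the problem and do not predict this trial. The weight is limited because the analysis is exploratory, but it serves a stated objective and is cheap to correct.

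**What to change.** In SAP 8.4.3.6:
- Keep whole-arm OS as randomized as the reference for Arms 2 and 3, and OS from first add-on dose as the description of the Add-on Treatment Set.
- Drop OS from randomization in the Add-on set and the analysis that excludes add-on patients. If they are kept, state beside each that the first contains guaranteed survival time and that the two must not be contrasted.
- If OS with versus without add-on is to be described, restrict it to Arm 2 and 3 patients with progression, start the clock at progression, and treat add-on as time-dependent, or use a landmark after progression. Name the progression date used; the BICR date is already derived for PFS. Label the result descriptive and subject to selection for add-on.

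The cost is SAP wording and modest programming with dates already collected. The analysis would have fewer patients and less precision: in the simulations with 40% to 90% uptake, 27% to 68% of an arm reached add-on, or about 12 to 31 of 45 (0.27 × 45 = 12.2; 0.68 × 45 = 30.6). Apparent survival with add-on will look less favourable than under summary 2.
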